2.1. Where will the research project be conducted? (Check all that apply)

- VA Inpatient Setting
- VA Laboratories
- University of Pennsylvania
- Other (Specify):

VA Outpatient Clinic/Office

Subject Homes

- Community Based Outpatient Clinics (CBOCs)

2.2. If research is conducted at a non-VA site, please specify where and how much of the project will be conducted at that location.

Section 3: Introduction

Provide scientific background and rationale for study. Including summary of gaps in current knowledge, relevant data, and how the study will add to existing knowledge. Chronic pain is a highly prevalent and costly condition in the US. An estimated 88.5 million adults suffer from daily pain, resulting in estimated cost of \$500-635 billion due to lost productivity, and \$261-300 billion in health care expenditures. To manage their chronic pain, 5 to 8 million Americans take an opioid medication daily. Yet, the risks associated with ongoing opioid prescription, including overdose, abuse and diversion, temper their analgesic effects. Opioids are not more effective in the treatment of chronic pain compared with non-opioid approaches. Current guidelines have adapted to the evidence, recommending opioid-sparing approaches for treating patients with chronic pain, and tapering for those on higher doses to safer levels of use. Tapering opioids, however, requires replacing them with effective non-opioid strategies. Improving mobility has been shown to improve pain and decrease medication use among patients chronically prescribed opiates. Concurrently, financial incentives and the use of behavioral incentives have been shown to promote mobility.

Appreciating the gains in health outcomes that can be made with “connected health” approaches, we propose a novel pilot study designed to evaluate if technology enabled care (TEC) strategies and financial incentives can improve patient mobility in our chronic pain population, reduce pain and decrease opioid use. Our primary aim is to determine if chronic pain patients who receive TEC-enhanced treatment with financial incentives demonstrate increased participation in activities that promote mobility (physical therapy, yoga, tai chi) in comparison to patients receiving usual care. Secondary outcomes will include whether increased activity participation also reduces pain severity and opioid use, and improves function and increases the number of daily steps taken. The results of this pilot will enable us to determine what strategies are effective at increasing mobility and if these gains translate into reduced pain and decreased opioid use. The Way to Health application, a research information technology platform at the University of Pennsylvania, will be used to track medication use.

Section 4: Objectives Section

4.1. Describe the study's purpose, specific aims, or objectives.

The objective of this pilot study to evaluate if behavioral incentives applied at the VA Medical Center can appreciably increase participation in activities that promote mobility, and subsequently reduce pain severity and opioid use.

Primary outcome: Activity participation (as measured by the Stanford Exercise Questionnaire) and increased mobility (as measured by wearable tracker).

Secondary outcomes: Opioid use (as measured by medication adherence and pill counts), physical function (as measured by PROMIS pain interference tool) and pain severity (as measured by PROMIS pain severity tool).

4.2. State the hypotheses to be tested.

Hypothesis: Behavioral financial incentives will lead to increased physical activity (as measured by the Stanford Exercise Questionnaire) and mobility (as measured by wearable tracker).

Section 5: Study Procedures

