Procedures. Eligible patients will be offered participation in this pilot study. The enrollment goal of 40 patients was chosen based on feasibility given the time-frame. Following informed consent, participants will be randomly assigned to one of the two study arms. All participants will be provided individual activity regimens, and be offered physical therapy, yoga, or tai-chi classes at the CMCVAMC. The activity goal will be participation in their activity regimen or classes at least twice per week, a frequency used in other studies promoting activity for chronic pain. Participants will self-report their activity, pain severity, functionality, and opioid use monthly via questionnaire and pill counts. Additionally, all participants will be provided an activity tracker to measure steps taken and instructed on use and data upload procedures. Upon the completion of their 12-week participation, participants are asked to complete an in-person exit survey answering questions about their experience in the study, the use of the FitBit activity watches, as well as the use of the FitBit application.

Those receiving the TEC-linked intervention will be familiarized with the text messaging process and the measures that will be administered via this technology. TEC will consist of a daily personalized text message from a dedicated research assistant reminding the patient to engage in their prescribed physical activity for the day. A second text message at the end of the day will direct the patient to return activity participation, pain severity, functionality, and opioid use data, and upload activity tracker data to the Way to Health (WTH) platform. The behavioral incentive provides the opportunity for subjects who meet their weekly activity goals to enter a lottery to receive either a small (\$30) or large (\$100) financial incentive. The lottery is structured such that subjects have an 18% chance/week of winning the small prize, and a 1% chance of winning the large prize. For those not meeting goals, they will be informed what they would have won had they met their goal. This design has been used in similar studies, with evidence showing the desire to avoid regret can be motivating.

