Measures. The validated NIH PROMIS measures will be utilized to measure key study outcomes. Opioid use will be collected via the WTH Medication Adherence measure and monthly pill counts, and physical activity collected by self-report and a wearable activity tracker. In addition to collection of baseline demographic data and study experience data, study measures will be administered at the specified time points to evaluate the efficacy of the TEC intervention:

Measure	Tool	TEC administration
---------	------	--------------------

Pain severity	PROMIS Pain Intensity	Daily via text
Function	PROMIS Pain Interference	Daily via text
Opioid use	Medication Adherence tool, Pill counts	Daily Beginning and End
Physical activity	Stanford exercise questionnaire Wearable activity tracker	Weekly via text Weekly download
Anxiety, depression, general well-being	PROMIS-29 profile PHQ9	Monthly Monthly

Investigative team: Our interdisciplinary team includes a wealth of experience, including nationally known researchers in chronic pain ([name]), as well as the medical director of the new Pain-PACT ([name]). In addition, our team boasts expertise in connected health interventions using behavioral incentives ([name]).

Study Timeline. Study start-up procedures, including IRB approval and development of text messaging intervention, will take place during the first 3 months of the funding period. Subject recruitment will begin in month 4 and end in month 7, with data collection completed by study month 10. Months 11 and 12 will be devoted to data analysis and dissemination activities.

5.1.2. **What research methods will be used in the project? *Check all that apply.***

 Surveys/Questionnaires	 Interviews	 Audio Taping
 Behavioral Observations	 Chart Reviews	 Video Taping
 Focus Groups	 Randomization	 Double-Blind
 Control Group	 Placebo	 Withhold/Delay Treatment
 Specimen Collection	 Deception	 Telephone Survey

X Other (Describe) Mobility tracking via a wearable device.

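### Opioid use is defined by adherence and pill counts, with no dose, tablet strength or quantity dispensed recorded, so a fall in the amount used can go unseen

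*Combined protocol and SAP*

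**What the plan says.** Section 4.1 gives the purpose as raising activity participation so as to "subsequently reduce pain severity and opioid use". The same section defines the secondary outcome as "Opioid use (as measured by medication adherence and pill counts". The Measures paragraph of 5.1.1 repeats this: "Opioid use will be collected via the WTH Medication Adherence measure and monthly pill counts". The Procedures paragraph adds, for all participants, "Participants will self-report their activity, pain severity, functionality, and opioid use monthly via questionnaire and pill counts". The TEC arm is also asked by text each day for opioid use data.

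The measures table in 5.1.1 lists the adherence tool and pill counts together, with the timing entry "Daily Beginning and End": the tool daily, the counts at the start and finish only.

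Section 9.2 compares change in opioid analgesic use between arms but defines no derived variable. Section 5.10.1 lists medication usage among the stored data without saying what it contains. In 5.1.2 the "Chart Reviews" box is not ticked. Section 3 describes current guidance as "recommending opioid-sparing approaches for treating patients with chronic pain, and tapering for those on higher doses to safer levels of use", and high-dose opioid therapy is an inclusion criterion.

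**The concern.** The question concerns an amount, but the named measures are not amounts. Adherence has the prescription as its denominator, so it loses information whenever the prescription itself changes. A pill count is a stock of tablets. It becomes consumption only when combined with what was dispensed, and becomes a dose only when combined with strength. Counts of different drugs or strengths cannot be averaged within an arm without a common unit.

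The enrolled patients are the group to whom the tapering guidance in Section 3 applies, so a changed prescription within 12 weeks is foreseeable, although no section makes it a study procedure. If it happens, the pilot may be unable to say whether opioid use fell, which is one of the questions it sets itself. Label details not noted when tablets are counted may be hard to recover later.

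**Working it through.** The plan states no figure for this outcome, and the 40 patients (20 per arm) were chosen for feasibility, so there is nothing to reproduce. The check applies three identities to assumed regimens.

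**Identities**
- Adherence = tablets taken / tablets prescribed.
- Tablets left = dispensed − taken.
- Daily use = tablets taken × strength / days.

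**Inputs.** All regimens are assumptions and none comes from the documents. The interval is 28 days, strength is in arbitrary units of one drug, dispensed equals prescribed, and the previous count is zero.

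| Case | Prescribed per day × strength | Taken per day | Adherence | Tablets taken | Left | Daily use |
|---|---|---|---|---|---|---|
| Reference | 6 × 15 | 6 | 100% | 168 | 0 | 90 |
| A: strength halved | 6 × 7.5 | 6 | 100% | 168 | 0 | 45 |
| B: fewer tablets prescribed | 4 × 15 | 4 | 100% | 112 | 0 | 60 |
| D: same prescription, fewer taken | 6 × 15 | 4 | 66.7% | 112 | 56 | 60 |
| E: more tablets, half strength | 8 × 7.5 | 8 | 100% | 224 | 0 | 60 |

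**Results against the reference**
- A: use changes by (45 − 90)/90 = −50%. Adherence, tablets taken and tablets left do not move.
- B: use changes by (60 − 90)/90 = −33%. Adherence and tablets left do not move. Tablets taken falls from 168 to 112, but this can be seen only if the quantity dispensed is recorded.
- D: use also falls 33%, and here both adherence and the leftover count move. With an unchanged prescription the count does track use.
- E: use falls 33% while tablets taken rises from 168 to 224. Tablet numbers without strength cannot be compared across products.

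**Does a dose-based variable recover the truth?** Use (previous count + dispensed − current count) × strength / days:
- A: (0 + 168 − 0) × 7.5 / 28 = 45
- B: (0 + 112 − 0) × 15 / 28 = 60
- D: (0 + 168 − 56) × 15 / 28 = 60
- E: (0 + 224 − 0) × 7.5 / 28 = 60

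All four match actual daily use.

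**Schedule.** Twelve weeks is 84 days. Counts at the start and finish give two counts and one interval, hence one average and no change over time. Counts every 28 days give 84 / 28 = 3 intervals. In neither case does the first count, taken alone, supply a pre-randomisation value, because no interval precedes it.

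**The case against.** The best reply is that the plan may already collect what is needed. The items and scoring of the adherence tool are not in the documents. Section 3 and 5.10.3 describe the Way to Health platform as recording medication use, all participants self-report opioid use monthly, and 9.2 speaks of opioid analgesic use rather than adherence. Any of these could include tablets taken. Pill counts are also a sound source: they track use when the prescription is stable, and the remedy itself is built from them. Tapering appears only as guideline background.

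All of this stands, and it limits the claim. It does not remove it, because no section says that such data form the outcome, names a unit, or provides for recording strength and quantity dispensed.

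A reader might go further and infer that the outcome will give the wrong sign, for example that a patient taking 4 of 6 prescribed tablets will be scored as deteriorating. The documents do not support that. They do not say that higher adherence is better or that lower adherence is worse, they do not make the raw leftover count the endpoint, and they do not show the tool. In that example both measures do respond, and the adverse reading would be supplied by the reader.

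**Conclusion.** The point holds as a mismatch between the aim and the stated measure. As written, the measures can fail to show a fall in opioid use when the prescription or tablet strength changes, and raw counts cannot be pooled across products. In the assumed cases, falls of 33% and 50% leave adherence and the leftover count unchanged. How often this would occur cannot be estimated, because the documents do not say how many prescriptions will change.

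The conclusion rests on two assumptions: that adherence carries its ordinary meaning, and that some prescriptions change within 12 weeks. The second is an inference from Section 3.

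The consequence is limited. This is a secondary outcome in a 40-patient pilot, the hypothesis in 4.2 covers only activity and mobility, and the primary comparison is unaffected. It should still be corrected before data collection, because the missing details are easiest to capture when the tablets are counted.

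**What to change.** - **Definition (4.1, 5.1.1, 9.2).** Define opioid use as the average daily amount taken per interval, in one common dose-equivalent unit: (previous count + dispensed − current count) × strength / days, with strength converted to that unit by a conversion named in advance. State that a lower value means less use.
- **Data.** At each count record drug, strength and quantity dispensed since the last count, in the same way in both arms. The TEC arm's daily text reports should not replace this.
- **Adherence.** Keep the tool as a separate descriptive measure.
- **Schedule.** Reconcile the monthly counts in the text of 5.1.1 with the start-and-finish counts in its table, since this decides how many intervals exist.
- **Baseline.** Take it from the enrolment prescription label or fill (drug, strength, quantity, fill date), converted to the same unit, and adjust the between-arm comparison for it. This reflects supply rather than tablets taken, but a fill dated before randomisation cannot be affected by the arm, so it is a legitimate covariate.

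The cost is a few extra fields at each count. If pharmacy records are used instead of the label, the "Chart Reviews" box in 5.1.2 must be ticked.

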5.1. Study Design

5.1.1. Describe in detail the experimental design, i.e. from recruitment procedures to study closure.

Design. Forty patients will be enrolled in the proposed work. Participants will be randomly assigned to one of two groups for the 12-week intervention period: (1) usual care; or (2) TEC strategies with enrollment in a weekly regret lottery.

Sample and Setting. The sample will be comprised of patients receiving care at the Corporal Michael Cresenz VA Medical Center (CMCVAMC) in Philadelphia as well as at the Pain-focused Patient Aligned Care Team (P-PACT). This primary care clinic was instituted to provide comprehensive, evidence-based care to patients with chronic non-malignant pain and on opioid therapy. Patients referred to the program are those identified as high-risk related to being on high dose opioid therapy; on combined opioid/benzodiazepine therapy; and/or having a history of substance abuse. A key component of the P-PACT program is improving mobility amongst patients using modalities available through the VA, including physical therapy, yoga and tai chi, which have an evidence base to improve pain, sleep, cognitive and physical function as well as decrease medication use.

Inclusion Criteria	Exclusion Criteria

• Chronic non-malignant pain• High dose opioid therapy• Possession of activated cell phone with text messaging capabilities• Willingness to comply with study requirements	
• Pain of malignant origin• Sensory impairments precluding use of text messaging and activity tracker• Physical disability precluding improvements in physical activity

Procedures. Eligible patients will be offered participation in this pilot study. The enrollment goal of 40 patients was chosen based on feasibility given the time-frame. Following informed consent, participants will be randomly assigned to one of the two study arms. All participants will be provided individual activity regimens, and be offered physical therapy, yoga, or tai-chi classes at the CMCVAMC. The activity goal will be participation in their activity regimen or classes at least twice per week, a frequency used in other studies promoting activity for chronic pain. Participants will self-report their activity, pain severity, functionality, and opioid use monthly via questionnaire and pill counts. Additionally, all participants will be provided an activity tracker to measure steps taken and instructed on use and data upload procedures. Upon the completion of their 12-week participation, participants are asked to complete an in-person exit survey answering questions about their experience in the study, the use of the FitBit activity watches, as well as the use of the FitBit application.

Those receiving the TEC-linked intervention will be familiarized with the text messaging process and the measures that will be administered via this technology. TEC will consist of a daily personalized text message from a dedicated research assistant reminding the patient to engage in their prescribed physical activity for the day. A second text message at the end of the day will direct the patient to return activity participation, pain severity, functionality, and opioid use data, and upload activity tracker data to the Way to Health (WTH) platform. The behavioral incentive provides the opportunity for subjects who meet their weekly activity goals to enter a lottery to receive either a small (\$30) or large (\$100) financial incentive. The lottery is structured such that subjects have an 18% chance/week of winning the small prize, and a 1% chance of winning the large prize. For those not meeting goals, they will be informed what they would have won had they met their goal. This design has been used in similar studies, with evidence showing the desire to avoid regret can be motivating.

Measures. The validated NIH PROMIS measures will be utilized to measure key study outcomes. Opioid use will be collected via the WTH Medication Adherence measure and monthly pill counts, and physical activity collected by self-report and a wearable activity tracker. In addition to collection of baseline demographic data and study experience data, study measures will be administered at the specified time points to evaluate the efficacy of the TEC intervention:

Measure	Tool	TEC administration
---------	------	--------------------

Pain severity	PROMIS Pain Intensity	Daily via text
Function	PROMIS Pain Interference	Daily via text
Opioid use	Medication Adherence tool, Pill counts	Daily Beginning and End
Physical activity	Stanford exercise questionnaire Wearable activity tracker	Weekly via text Weekly download
Anxiety, depression, general well-being	PROMIS-29 profile PHQ9	Monthly Monthly

Investigative team: Our interdisciplinary team includes a wealth of experience, including nationally known researchers in chronic pain ([name]), as well as the medical director of the new Pain-PACT ([name]). In addition, our team boasts expertise in connected health interventions using behavioral incentives ([name]).

Study Timeline. Study start-up procedures, including IRB approval and development of text messaging intervention, will take place during the first 3 months of the funding period. Subject recruitment will begin in month 4 and end in month 7, with data collection completed by study month 10. Months 11 and 12 will be devoted to data analysis and dissemination activities.

5.1.2. **What research methods will be used in the project? *Check all that apply.***

 Surveys/Questionnaires	 Interviews	 Audio Taping
 Behavioral Observations	 Chart Reviews	 Video Taping
 Focus Groups	 Randomization	 Double-Blind
 Control Group	 Placebo	 Withhold/Delay Treatment
 Specimen Collection	 Deception	 Telephone Survey

X Other (Describe) Mobility tracking via a wearable device.

5.1.3. **Provide description of the study population (delineate all categories of subjects – male, female, inpatients, outpatients, providers, family members, employees, etc.). Include anticipated initial enrollment numbers (and number of subjects anticipated to complete all aspects of the protocol).**

The study population will include 40 participants total: 1) adults age 18 years or older; 2) Chronic non-malignant pain; 3) High dose opioid therapy; 4) Possession of activated cell phone with text messaging capabilities; and 5) willingness to comply with study requirements.

5.1.4. **As applicable, provide rationale and information on any added protections and safeguards for vulnerable populations (children, prisoners, pregnant women, physically or mentally-disabled persons, and economically or educationally disadvantaged persons).**

This will not include children or prisoners. For other vulnerable populations, this study will only include subjects wishing to participate. Those individuals with sensory impairments precluding use of text messaging and activity tracker, or with physical disability precluding improvements in physical activity will not be included in the study.

5.1.5. Does this project target a specific race or ethnic group as subjects? **NOT APPLICABLE**
If yes, check all that apply.

Race

Ethnicity

- American Indian or Alaska Native
- Asian
- Black or African American
- Native Hawaiian or other Pacific Islander
- White
- Other

- Hispanic or Latino
- Not Hispanic or Latino

